5. TREATMENTS ADMINISTERED

5.1. Treatments Administered

Participants will receive voxelotor as 500 mg tablets. Detailed instructions will be provided to participants prior to the first dose of study drug.

5.2. Dose Frequency

Participants will receive voxelotor tablets administered orally, once or twice daily, as outlined in Section 3.2. If a participant misses a dose, the participant should resume normal dosing the next day (ie, the dose, on the day after the day of a missed dose, should not be increased or decreased).

5.3. Physical Description of Voxelotor

Voxelotor is a synthetic small molecule bearing the chemical name 2-hydroxy-6-((2-(1-isopropyl-1H-pyrazol-5-yl)pyridin-3-yl)methoxy)benzaldehyde. The chemical formula is C₁₉H₁₉N₃O₃ and the molecular weight is 337.4 g/mol.

5.4. Formulation

Voxelotor will be supplied as 500 mg tablets.

Details regarding drug administration will be provided in the Pharmacy Manual.

5.5. Packaging and Labeling

Voxelotor drug product will be supplied to clinical sites in high-density polyethylene bottles with induction sealed polypropylene child-resistant caps. At each visit (except for End of Treatment and EOS), participants will be supplied a sufficient quantity of study drug to ensure continuous dosing through to the next clinic visit. All study drug packaging must be returned at each visit, regardless if they are empty or contain unused study drug.

5.6. Investigational Product Supply

GBT or their representative will supply the packaged and labeled drug product to the investigational sites. Additional details are provided in the Pharmacy Manual.

5.7. Storage and Handling Procedure

All study medications will be stored at controlled room temperature between 15°C to 25°C (59°F to 77°F), in the storage area of the investigational site pharmacy, which is a secure, temperature controlled, locked environment with restricted access. The Sponsor or its representatives will be permitted upon request to audit the supplies, storage, dispensing procedures, and records.

5.8. Concomitant and Prohibited Medications

5.8.1. Prior and Concomitant Medications

A concomitant medication is defined as any prescription or over-the-counter preparation, including vitamins and supplements.

In the interests of participant safety and acceptable standards of medical care, the Investigator will be permitted to prescribe treatment(s) at his/her discretion. For all study participants, all administered concomitant medications from signing the ICF until 28 days (4 weeks) after the participant's last dose of study drug, must be recorded on the participant's case report form (CRF).

All reported prior and concomitant medications will be coded using the current version of the World Health Organization (WHO) Drug Dictionary.

5.8.2. Hydroxyurea Therapy

Hydroxyurea therapy is allowed, provided that the dose has been stable for at least 90 days prior to signing the ICF. Participants who start chronic therapy with HU any time after enrollment will be discontinued from the study.

Participants who are on HU may have their dose adjusted (based on change in their weight) if the mg/kg dose is stable.

5.8.3. Transfusion

Participants who require chronic transfusion will be discontinued from study drug and 28 days later undergo the EOS visit.

5.8.4. Other Therapies

Penicillin prophylaxis and vaccinations are allowed as per standard of care.

Other concomitant medications are allowed, unless the restrictions in Section 5.8.5 and Section 5.8.6 apply. Permitted concomitant medications include folic acid, L-glutamine, over-the-counter analgesics, and opioids.

The use of erythropoietin is prohibited during the study.

5.8.5. Concomitant Medications to Be Used with Caution

Voxelotor may increase the plasma concentrations of CYP3A4 substrates with a narrow therapeutic index and should be used with caution with these medications. See [Table 1](#) for examples.

Table 1: CYP Substrates with Narrow Therapeutic Range

CYP Enzymes	Substrates with Narrow Therapeutic Range
CYP3A4	Alfentanil, cyclosporine, dihydroergotamine, ergotamine, fentanyl, pimozide, quinidine, sirolimus, and tacrolimus,

CYP, cytochrome P450; FDA, Food and Drug Administration.

Note that this is not an exhaustive list; country specific lists may be used if available. Decision can be made in consultation with the Sponsor's Medical Monitor.

Substrates with a "narrow therapeutic range" refers to drugs whose exposure-response relationship indicates that small increases in their exposure levels by the concomitant use of CYP inhibitors may lead to serious safety concerns. Adapted from: FDA DRAFT Guidance for Industry: Drug Interactions Studies-Study Design, Data Analysis, Implications for Dosing, and Labeling Recommendations. February 2012. Restrictions.

5.8.6. Prohibited Concomitant Medications

Use of an investigational product other than that under study in this trial, regardless of its intended use, is prohibited throughout the trial and for 28 days after the last dose. Additionally, concomitant medications (eg, crizanlizumab) that confound the ability to interpret data from the study are prohibited.

Voxelotor is a moderate CYP3A4 inhibitor and should not be coadministered with sensitive CYP3A4 substrates with a narrow therapeutic index (refer to Table 2 for examples).

Table 2: Sensitive CYP3A4 Substrates with Narrow Therapeutic Range

Sensitive CYP3A4 Substrates with Narrow Therapeutic Range
Alfentanil, sirolimus, and tacrolimus

CYP, cytochrome P450.

Note: **This is not an exhaustive list.** Country-specific lists may be used if available.

For an updated list, refer to the following link:

<https://www.fda.gov/Drugs/DevelopmentApprovalProcess/DevelopmentResources/DrugInteractionsLabeling/ucm093664.htm#table 3-2>.

Voxelotor should not be coadministered with strong CYP3A4 inhibitors (refer to Table 3 for examples) or fluconazole.

Table 3: Examples of Strong CYP3A4 Inhibitors

CYP	Strong Inhibitors
CYP3A4	Boceprevir, ceritinib, clarithromycin, cobicistat, conivaptan, danoprevir/ritonavir, elvitegravir/ritonavir, grapefruit juice, idelalisib, indinavir/ritonavir, itraconazole, ketoconazole, lopinavir/ritonavir, mibefradil, mifepristone, nefazodone, neflifavir, posaconazole, ribociclib, ritonavir, saquinavir/ritonavir, telaprevir, telithromycin, tipranavir/ritonavir, troleandomycin, Vickira Pak®, voriconazole

CYP, cytochrome P450.

Note: **This is not an exhaustive list.** Country-specific lists may be used if available.

For an updated list, refer to the following link:

<https://www.fda.gov/Drugs/DevelopmentApprovalProcess/DevelopmentResources/DrugInteractionsLabeling/ucm093664.htm#table 3-2>.

Since CYP3A4 is a primary CYP responsible for the metabolism of voxelotor, concomitant use of voxelotor and moderate or strong inducers of CYP3A4 is not allowed (refer to Table 4 for examples).

Table 4: Examples of Moderate and Strong CYP Inducers

CYP3A4	Examples
Moderate CYP3A4 inducers	Efavirenz, bosentan, etravirine, phenobarbital, and primidone
Strong CYP3A4 inducers	Rifampin, apalutamide, phenytoin, carbamazepine, enzalutamide, St John's wort, and mitotane

CYP, cytochrome P450.

Note: **This is not an exhaustive list.** Country-specific lists may be used if available.

For an updated list, refer to the following link:

<https://www.fda.gov/Drugs/DevelopmentApprovalProcess/DevelopmentResources/DrugInteractionsLabeling/ucm093664.htm#table3-3>.

Additional prohibited medications are shown in Table 5.

Table 5: Additional Prohibited Medications

Prohibited Medications
Astemizole, cisapride, terfenadine, crizanlizumab

6. FERTILITY/CONTRACEPTIVE REQUIREMENTS

All female participants of child-bearing potential (post menarche) should avoid pregnancy, and all sexually active male participants should avoid fathering a child.

6.1. Instructions for Female Participants of Child-Bearing Potential

For female participants of child-bearing potential (post menarche) and sexually active, pregnancy should be avoided by either abstinence from sex/sexual intercourse or the use of highly effective means of contraception for the duration of the study, and for a total period of 30 days after the participant has taken her last dose of voxelotor. Highly effective means of contraception are listed below in Section 6.4. Pregnancy reporting requirements are outlined in Section 9.4.

Female participants who become pregnant during the study will be withdrawn from the study.

6.2. Female Participants of Non-Child-Bearing Potential

Female participants of non-child-bearing potential are defined as: bilateral oophorectomy/hysterectomy/postmenopausal females being amenorrheic for greater than 2 years with an appropriate clinical profile, eg, age appropriate, history of vasomotor symptoms.

6.3. Instructions for Male Participants Capable of Fathering a Child

There is no information about effects that voxelotor could have on the development of the fetus in humans. Therefore, it is important that the partners of male participants do not become pregnant during the study and for a total period of 30 days after the male participant has taken the last dose of voxelotor.

As a precaution, all male participants who are sexually active should avoid fathering a child by either true abstinence or the use of barrier methods of contraception.

6.4. Acceptable Forms of Contraception for Sexually Active Participants

For female participants:

Highly effective methods of birth control are defined as those which result in a low failure rate (ie, less than 1% per year) when used consistently and correctly. Highly effective methods of birth control are as follows:

1. Hormonal contraceptives
 - a. Combined (estrogen and progestogen containing) hormonal contraception associated with inhibition of ovulation:
 - Oral
 - Intravaginal
 - Transdermal
 - b. Progestogen-only hormonal contraception associated with inhibition of ovulation:
 - Oral
 - Injectable
 - Implantable

- c. Hormonal contraception must be supplemented with a barrier method (preferably male condom).
2. Intrauterine device (IUD)
3. Intrauterine hormone-releasing system (IUS)
4. Bilateral tubal occlusion
5. Sexual abstinence:

Sexual abstinence is considered a highly effective method only if the participant is refraining from heterosexual intercourse during the entire period of risk associated with the study drug. The reliability of sexual abstinence needs to be evaluated in relation to the duration of the clinical study and the preferred and usual lifestyle of the participant.

For male participants with female partners capable of reproduction:

Barrier methods of contraception:

- Condom with occlusive cap (diaphragm or cervical/vault caps) with spermicidal foam/gel/film/cream/suppository for female partner. The use of barrier contraceptives should always be supplemented with the use of a spermicide.

7. ASSESSMENT OF TREATMENT COMPLIANCE

Drug disposition records will be maintained, specifying the amount dispensed to each participant and the date of dispensation. This record will be available for Sponsor review at any time.

Compliance will be determined by returned tablet count.

8. STUDY PROCEDURES AND EVALUATIONS

The Screening Period for a participant commences at the point at which the participant undergoes the first study-specific screening assessment. All screening assessments must be completed within 30 days before the first dose of study drug.

The required study procedures, and timing that they need to occur, are outlined in the Schedule of Assessments ([Appendix A](#), [Appendix B](#)).

8.1. Informed Consent

A signed and dated consent form will be obtained before any protocol-specified screening procedures are performed.

Guidelines for the informed consent process are outlined in Section [13.6](#).

8.2. Participant Study Number

Upon execution of consent, all participants will be given a unique study number. This number will be used to identify the participant throughout the clinical study and must be used on all study documentation related to that participant. A new participant number will be assigned to rescreened participants.

8.3. Demographics and Medical and Medication History

Demographic and baseline characteristics of sex, race, ethnicity, age, weight, and height of the participant will be collected at the time of Screening.

Medical history includes clinically significant diseases, surgeries, all medications (eg, prescription drugs, over-the-counter drugs, herbal/homeopathic remedies, nutritional supplements) used by the participant within 30 days prior to the first dose will be recorded.

8.4. Physical Examination

The physical examination (PE) will be a complete PE according to the standard at the site for this age group at Screening and an abbreviated, symptom-directed examination at the scheduled clinic visits.

- Complete PE should include at a minimum: Examination of head, eyes, ears, nose, and throat, skin, cardiovascular and respiratory systems, abdominal examination, neurologic, musculoskeletal, and symptom-directed examination.
- Abbreviated PE should include at a minimum: Examination of skin, cardiovascular and respiratory systems, abdominal examination, and symptom-directed examination.

8.5. Vital Signs

Vital signs (blood pressure, heart rate, and temperature will be measured, as outlined in Schedule of Assessments ([Appendix A](#), [Appendix B](#)), after a participant has rested comfortably for at least 5 minutes in the supine or sitting position, as age appropriate and feasible. A repeated measurement of any of the vital signs parameters will be taken within 5 minutes if the first reading is outside of the normal range and deemed clinically significant.

8.6. Body Mass Index

Height and weight will be measured, and body mass index (BMI) will be calculated.

8.7. Electrocardiograms

Electrocardiograms (12-lead) will be recorded after 10 minutes of rest in the supine position. ECGs recorded at Screening, on Days 1 and 7 of each period, and Day 21 in Period 4 will be recorded in triplicate for evaluation at a central ECG laboratory (refer to the Schedule of Assessments, [Appendix A](#), [Appendix B](#)). Other ECGs will be recorded as singles.

8.8. Eligibility Assessment, Inclusion/Exclusion Review

Eligibility assessments will be conducted during screening and prior to receiving study drug on treatment Day 1. If a participant is found to meet the inclusion/exclusion criteria, but then has a clinically significant change in status prior to administration of the first dose of study drug (eg, is hospitalized for sickle cell crisis), the participant should be considered a screen failure. Participants who have not been enrolled or dosed may be rescreened once at the Investigator's discretion and in consultation with the Sponsor. Participants who rescreen will have all SCREENING assessments redone, except for Hb genotyping.

8.9. Adverse Events and Concomitant Medications

AEs and concomitant medications will be recorded throughout the study. See Section [9.2](#) for details regarding AE reporting period for this study.

8.10. Clinical Global Impression of Change

Investigator's assessment of change in the overall health condition of the participant. The CGI-C assessment will be performed using a 7-point scale to assess how much the participant's SCD has improved or worsened relative to Baseline.

8.11. Patient Global Impression of Change

The participant's assessment of change in their overall health condition. The PGI-C assessment will be performed using a 7-point scale to assess how much the participant's SCD has improved or worsened relative to Baseline.

8.12. Safety Laboratory Assessments

Refer to the Schedule of Assessments ([Appendix A](#), [Appendix B](#)) for the specific timing that laboratory tests are to occur and refer to the Laboratory Manual for details.

It is the responsibility of the Investigator or designee to assess the clinical significance of all abnormal clinical laboratory values as defined by the applicable list of normal values on file (ie, local laboratory). All clinically significant laboratory value abnormalities are to be recorded as AEs.

Additional and repeat laboratory safety testing for the evaluation of abnormal results and/or AEs during the study may be performed at the discretion of the Investigator or upon request of the Sponsor. Repeat laboratory testing of abnormal potentially clinically significant or clinically

significant results for the screening evaluation of the participant may be repeated at the discretion of the Investigator.

8.12.1. Screening

In addition to screening laboratory tests that are also conducted throughout the study, the following laboratory assessments will be conducted at Screening only:

- Follicle-stimulating hormone (FSH) (postmenopausal females only)
- Coagulation panel (prothrombin time [PT], partial thromboplastin time [PTT], international normalized ratio [INR])
- Serology panel: Serum virology (hepatitis A, B, C, and, if clinically indicated, HIV)
- Hemoglobin genotyping (only if no documentation of hemoglobin genotype is available)
- Fetal hemoglobin
- Urinalysis: urine will be assessed for color and appearance. Dipstick analysis will be conducted for specific gravity, pH, protein, glucose, ketones, leucocytes, bilirubin, urobilinogen, nitrite, and occult blood. Microscopic analysis (RBCs, white blood cells [WBCs], bacteria, and casts) will be collected as clinically indicated.

8.12.2. Hematology

Hematology assessments include the following:

- RBCs
- Hematocrit
- Hb
- Platelets
- WBCs with differential (basophils, eosinophils, neutrophils, monocytes, and lymphocytes)
- Percent and absolute reticulocytes
- Mean corpuscular volume (MCV)
- Mean corpuscular hemoglobin concentration (MCHC)

8.12.3. Serum Chemistry

Chemistry assessments include the following:

- ALT
- Albumin
- Alkaline phosphatase (ALP)
- Aspartate aminotransferase (AST)

- Bicarbonate
- Blood urea
- Chloride
- Calcium
- Creatinine
- Glucose
- LDH
- Sodium
- Potassium
- Bilirubin (total, direct, and indirect)

8.13. Other Laboratory Assessments

8.13.1. Effect on Hemoglobin Oxygen Equilibrium Curve

Assessments of P50 and P20 will be conducted by hemoximetry as indicated in the Schedule of Assessments ([Appendix A](#), [Appendix B](#)).

8.13.2. Hemoglobin Genotype

Unless documented in their medical record, participants will be tested for hemoglobin genotype at Screening.

8.13.3. Serum Erythropoietin

Serum erythropoietin will be measured as indicated in the Schedule of Assessments ([Appendix A](#), [Appendix B](#)).

8.13.4. Red Blood Cell Deformability and Dense Cells

Assessments will be conducted as indicated in the Schedule of Assessments ([Appendix A](#), [Appendix B](#)).

8.13.4.1. Pregnancy Test

Pregnancy tests will be performed on female participants who are post menarche; a serum pregnancy test (human chorionic gonadotropin in serum) will be performed at Screening. Urine pregnancy tests will be performed in females who are post menarche as outlined in the Schedule of Assessments ([Appendix A](#) and [Appendix B](#)). If a urine test is positive, the result must be confirmed with a serum pregnancy test.

Information regarding fertility and contraceptive requirements is provided in Section [6](#); highly effective means of contraception are listed in Section [6.4](#). Instructions for reporting pregnancy are provided in Section [9.4](#).

8.13.5. Pharmacokinetic Sample Collection

Blood samples for whole blood and plasma PK assessments will be collected according to the Schedule of Assessments ([Appendix A](#), [Appendix B](#)). Whole blood and plasma concentrations of voxelotor will be measured using a validated liquid chromatography mass spectrometry (LCMS) assay.

8.14. Phone Call

Follow-up phone calls will be conducted on Day 3 of each study period ([Appendix A](#), [Appendix B](#)). These phone calls will be used to confirm compliance, ask for concomitant medications, and check for participant wellbeing by asking open ended questions (eg, How are you feeling?).

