3.6. Duration of Study Participation and of the Study

Study participation will be up to 44 weeks in duration, which includes up to 30 days in the Screening Period; 21 days (3 weeks) each in Periods 1, 2, 3, and 4; 168 days (24 weeks) in the Observation Period; and 28 days in the Safety Follow-up Period. See Section 3.2 for additional information regarding the study periods for this study.

The study will end when the last participant's last visit occurs.

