9. ADVERSE AND SERIOUS ADVERSE EVENTS

Safety assessments will consist of recording all AEs and SAEs, protocol-specified hematology and clinical chemistry variables, clinical examination findings, measurement of protocol-specified vital signs, and the results from other protocol-specified tests that are deemed critical to the safety evaluation of voxelotor.

The determination, evaluation, reporting, and follow-up of AEs will be performed as outlined in Section 9.1. At each visit, the study participant or participant caregiver will be asked about any new or ongoing AE since the previous visit. Assessments of AEs will occur at each study visit. See Section 9.2 for details regarding the required time periods for AE reporting.

Clinically significant changes from study baseline in physical examination findings, weight, vital signs, and clinical laboratory parameters will be recorded as AEs or SAEs, as appropriate.

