10.4. Data Analysis

Data will be presented by maximum dose level.

A TEAE, defined as an event that occurs on or after Day 1 of study drug or the worsening of a pre-existing condition on or after Day 1 of study drug, will be classified according to the Medical Dictionary for Regulatory Activities (MedDRA). The incidence of TEAEs and relatedness to study drug, as assessed by the Investigator, will be summarized descriptively by maximum dose level tolerated.

Clinical laboratory tests, ECGs, and vital signs over time will be summarized by maximum dose level tolerated using descriptive statistics. Change from baseline in ECG intervals will be evaluated using descriptive statistics. If an effect on mean change from baseline in QTc interval exceeding 10 msec is observed, concentration-QTc analysis may be explored. Results from the diagnostic interpretation will be summarized by maximum dose tolerated.

An Hb responder endpoint, defined as an increase in Hb of > 1 g/dL compared to Baseline, will be summarized. Additionally, change from baseline in hemoglobin and clinical measures of hemolysis (unconjugated bilirubin, % reticulocyte, absolute reticulocyte, and LDH) will be summarized by maximum dose level tolerated using descriptive statistics.

The incidence of VOCs will be summarized by maximum dose tolerated.

The CGI-C and PGI-C will be summarized by maximum dose level tolerated.

Population PK analysis using nonlinear mixed-effect modeling will be performed to characterize voxelotor PK in plasma, and whole blood.

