APPENDIX A. SCHEDULE OF ASSESSMENTS: DOSE ESCALATION PHASE

Visit (days)	Screening	Periods 1, 2, 3, and 4					Period 4 Only
	Day -21 to Day -1	Day 1	Day 2	Day 3	Day 7 ± 1	Day 14 ± 2	
Visit to investigational site	X	X	X		X	X	X
Phone call				X			
Informed consent	X						
Review inclusion/exclusion criteria	X	X					
Medication and medical history	X	X					
Height ^a /weight/BMI	X	X					X
Vital signs ^b	X	X	X			X	
ECG (12-lead) in triplicate ^c	X	X			X		X
Physical examination ^d	X	X					
Serum pregnancy test (females of child-bearing potential only)	X						
Urine pregnancy test (females of child-bearing potential only) ^e		X					
FSH (postmenopausal females only)	X						
Coagulation panel (PT, PTT, INR)	X						
Serology panel (Hepatitis A, B, C, and HIV ^f)	X						
Blood for hematology and chemistry	X	X	X			X	X
Hemoglobin genotype testing (if not already available)	X						
Fetal hemoglobin	X						
Urinalysis	X						
Erythropoietin		X					
RBC deformability, dense cells (if feasible)		X					
Hemoximetry (P50 and P20) ^g		X	X		X		X
Study drug administration ^{h,i}		→					
Blood for PK assessment ^j		X	X		X		X
CGI-C and PGI-C		X ^k					X

Visit (days)	Screening	Periods 1, 2, 3, and 4					Period 4 Only
	Day -21 to Day -1	Day 1	Day 2	Day 3	Day 7 ± 1	Day 14 ± 2	Day 21
Concomitant medications	X	X	X	X	X	X	X
Adverse events	X	X	X	X	X	X	X

BID, twice daily; BMI, body mass index; CGI-C, Clinical Global Impression of Change; ECG, electrocardiogram; FSH, follicle-stimulating hormone; HIV, human immunodeficiency virus; INR, international normalized ratio; P20, partial pressure at which hemoglobin is 20% saturated with oxygen; P50, partial pressure at which hemoglobin is 50% saturated with oxygen; PGI-C, Patient Global Impression of Change; PK, pharmacokinetic; PT, prothrombin time; PTT, partial thromboplastin time; RBC, red blood cell.

Note: For procedures scheduled to be performed at the same timepoint, the order of assessments is as follows: vital signs, PK sample collection, blood draw for PD/safety laboratory assessments, ECGs. If times are delayed due to technical difficulties, this will be noted but not considered a protocol violation. RBC deformability and dense cells will be tested if feasible by the local or collaborating lab at the time of collection.

^a Height to be assessed at Screening only.

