^j On Day 1, blood samples for PK will be obtained predose (within 30 minutes prior to dosing) and at 2 hours (± 15 min) and 8 hours (± 15 min) postdose. On Day 2, blood samples for PK will be obtained predose only, and on Day 7, will be obtained predose and 2 hours postdose. The predose sample will be obtained prior to morning dosing at the investigational site.

^k Periods 2, 3, and 4 only (equivalent to Day 21 for Periods 1, 2, and 3, respectively).

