APPENDIX B. SCHEDULE OF ASSESSMENTS: OBSERVATION PERIOD AND SAFETY FOLLOW-UP

Visit (weeks)	Observation Period							Safety Follow-up ^a
	Week 1		Week 3	Week 6	Week 12	Week 18	Week 24/ EOT	
Visit (days)	Day 1 ^b	Day 7	Day 21	Day 42	Day 84	Day 126	Day 168	Day 196
Visit to investigational site	X	X	X	X	X	X	X	X
Weight/BMI							X	X
Vital signs ^c		X	X	X	X	X	X	X
ECG (12-lead) in triplicate ^d					X		X	X
Physical examination ^e							X	X
Urine pregnancy test (females of child-bearing potential only) ^f		X			X		X	
Blood for hematology and chemistry		X	X	X	X	X	X	X
Urinalysis							X	
Erythropoietin							X	
RBC deformability, dense cells (if feasible)					X		X	
Hemoximetry (P50 and P20) ^g		X	X		X		X	
Study drug administration ^{h,i}	→							
Blood for PK assessment ^j		X	X		X		X	
CGI-C and PGI-C					X		X	
Concomitant medications		X	X	X	X	X	X	X
Adverse events		X	X	X	X	X	X	X

BMI = body mass index; CGI-C, Clinical Global Impression of Change; ECG, electrocardiogram; EOS, End of Study; EOT, End of Treatment; P20, partial pressure at which hemoglobin is 20% saturated with oxygen; P50, partial pressure at which hemoglobin is 50% saturated with oxygen; PGI-C, Patient Global Impression of Change; PK, pharmacokinetic; RBC, red blood cell.

Note: For procedures scheduled to be performed at the same timepoint, the order of assessments is as follows: vital signs, PK sample collection, blood draw for PD/safety laboratory assessments, ECGs. If times are delayed due to technical difficulties, this will be noted but not considered a protocol violation. RBC deformability and dense cells will be tested if feasible by the local or collaborating lab at the time of collection.

^a Safety Follow-up visit will take place 28 days post final dose.

^b Day 1 of the observation period is the same as the last day of the dose escalation period. If the participant begins the observation period after a dose reduction, a Day 1 clinical visit is needed, which would collect the same assessments as the Day 21 visit in the Dose Escalation Period (Appendix A).

^c Vital signs (heart rate and blood pressure) will be obtained in the morning prior to dosing and other planned assessments.

^d Single safety ECG at Week 12, Week 24/ET, and Week 196 (EOS).

^e Physical examinations may be abbreviated. Abbreviated physical examination should include at a minimum: Examination of skin, cardiovascular and respiratory systems, abdominal examination, and symptom-directed examination.

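### Section 10.4 plans one whole-study TEAE incidence by maximum dose tolerated, although scheduled AE contacts fall from about 1.67 to 0.25 per week after escalation, so the table cannot give the dose comparison that Section 1.5.1 sets out

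*Combined protocol and SAP*

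**What the plan says.** Section 9 ties the asking about AEs to visits: "Assessments of AEs will occur at each study visit", and each visit covers new or continuing events over the interval just ended. In Appendix A the AE row reads "Adverse events X X X X X X X". The seven marks are Screening, then Days 1, 2, 3 (the phone call), 7 and 14 of every escalation period, then Day 21 in Period 4 only. A footnote to that schedule treats Day 1 of Periods 2 to 4 as the closing day of the period before.

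Appendix B, "SCHEDULE OF ASSESSMENTS: OBSERVATION PERIOD AND SAFETY FOLLOW-UP", marks AEs on Days 7, 21, 42, 84, 126 and 168, and at follow-up on Day 196. Its Day 1 cell is blank. A footnote explains that "Day 1 of the observation period is the same as the last day of the dose escalation period", with a separate Day 1 visit only after a dose reduction. Section 3.6 gives the lengths: "21 days (3 weeks) each in Periods 1, 2, 3, and 4; 168 days (24 weeks) in the Observation Period".

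Section 9.2.1 requires all AEs to be recorded from consent to 28 days after the last dose, and SAEs to be reported within 24 hours of awareness.

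Section 10.4 counts every event from Day 1 of study drug as treatment-emergent and states: "The incidence of TEAEs and relatedness to study drug, as assessed by the Investigator, will be summarized descriptively by maximum dose level tolerated". It names no breakdown by phase, period or dose at onset.

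Section 8.14 states "Follow-up phone calls will be conducted on Day 3 of each study period" and cites both appendices. Appendix B has neither a phone-call row nor a Day 3 column.

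**The concern.** TEAEs and SAEs are the primary endpoint (Section 10.1.1). Section 1.5.1 says the study is to assess tolerability and safety above 1500 mg and to compare the results with 1500 mg. It also reports that earlier treatment-related AEs were mostly low-grade gastrointestinal events, the kind a participant may not remember after six weeks.

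A participant who escalates takes each lower dose only under frequent contact. The final dose is taken for 3 + 24 = 27 weeks, of which 24 are under infrequent contact. A lower event rate at the final dose could therefore partly reflect how often participants were asked.

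The planned table does not help. It places an event that began at 1500 mg in Period 1 in the row of whatever dose the participant finally tolerated, and it adds together events collected under two very different schedules.

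**Working it through.** The documents state no contact rate, so there is no figure of theirs to reproduce. The inputs are the AE rows of Appendices A and B and the durations in Section 3.6.

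**1. Contact rates**
- Escalation: 5 contacts / 3 weeks = 1.67 per week. Period 4: 6 / 3 = 2.0. All four periods: (4 × 5 + 1) / 12 = 21 / 12 = 1.75.
- Observation: 6 / 24 = 0.25 per week.
- Ratio: 1.67 / 0.25 = 6.7.

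**2. Gaps between contacts**
- Escalation, nominal days: 1, 1, 4, 7, then 7 or 8 to the next Day 1. The windows (Day 14 ± 2, period length ± 3 days) allow up to 24 − 12 = 12 days.
- Observation, from Day 1: 6, 14, 21, 42, 42, 42. The three long gaps cover 126 of 168 days, or 75%.

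**3. Share of treatment time, for a participant completing all four periods**
- Observation is 24 of 36 weeks (67%) but 6 of 21 + 6 = 27 on-treatment contacts (22%).

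**4. Contrast between the planned groups.** Assume that the period at the dose not tolerated is completed, that one visit closes escalation, and that observation lasts the full 24 weeks.

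| Maximum dose tolerated | Contacts | Weeks | Per week |
|---|---|---|---|
| 3000 mg | 20 + 1 + 6 = 27 | 36 | 0.75 |
| 2500 mg | 20 + 1 + 6 = 27 | 36 | 0.75 |
| 2000 mg | 15 + 1 + 6 = 22 | 33 | 0.67 |
| 1500 mg | 10 + 1 + 6 = 17 | 30 | 0.57 |

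The extremes differ by 0.75 / 0.57 = 1.3, with the higher-dose groups seen more often. If instead the period at the dose not tolerated stops after one week (contacts on Days 1, 2, 3 and 7), the 1500 mg group has 5 + 4 + 1 + 6 = 16 in 28 weeks (0.57) and the 2500 mg group 15 + 4 + 1 + 6 = 26 in 34 weeks (0.76). The ratio is again about 1.3.

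**5. Contrast within a participant.** For one who reaches 3000 mg, contacts at that dose are 6 + 6 = 12 in 27 weeks, or 0.44 per week, against 1.67 at each lower dose: a ratio of 1.67 / 0.44 = 3.8. Comparing observation alone with a lower dose, the ratio is the 6.7 of step 1.

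**6. Effect of the missing call.** Adding a Day 3 call to observation gives 7 / 24 = 0.29 per week. The ratio in step 1 becomes 1.67 / 0.29 = 5.7, and the three 42-day gaps remain.

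**7. Illustration of possible loss (assumption only).** Suppose the chance of reporting a transient event decays exponentially with time since it occurred, with half-life h and k = ln 2 / h. The share reported is Σ[(1 − e^(−kL)) / k] / ΣL over the gaps L in step 2, using 8 days for the last escalation gap. For h = 14 days this gives 86% in escalation and 49% in observation. For h = 112 days it gives 98% and 90%. The reported rate in observation would be roughly 0.6 to 0.9 of that in escalation with no true difference. The documents give no recall figure, so this shows direction and a possible range, not an estimate.

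**The case against.** The strongest reply is that Section 10.4 does not compare the doses a participant passed through. It groups participants by maximum dose tolerated, and every group has the same observation schedule. A reader might infer that the 6.7-fold drop makes the highest-dose group look safer in that table. The documents do not support this: step 4 gives about 1.3-fold, in the other direction. This part of the reply stands.

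A reader might also infer that AEs in observation are in fact under-recorded. The documents do not show it. Each visit covers the whole interval since the last, recording is continuous, and SAE reporting does not wait for a visit. What remains is a recall risk for mild, transient events over gaps of up to 42 days. Neither schedule lists a diary that would reduce it.

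A third tempting reading is that the absent phone call explains the drop in contacts. Step 6 shows that it does not: the call would fall four days before the Day 7 visit. The mismatch itself is open to an innocent reading, since Section 8 cites both appendices almost by habit and the phrase may mean Periods 1 to 4 only. Section 8.7, for example, describes Day 7 ECGs in each period with the same pair of citations, and Appendix B has no Day 7 ECG. Against that, Section 3.2 lists the Observation Period alongside Periods 1 to 4, so the text remains ambiguous.

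Finally, close contact at each new dose and lighter contact afterwards is a reasonable design for an exploratory, descriptive study. That is accepted. The point concerns the summary, not the visit schedule.

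**Conclusion.** The concern holds in limited form. AE contact frequency differs 6.7-fold between phases, and Section 10.4 summarizes both together by maximum dose tolerated. The planned between-group contrast is little affected, at about 1.3-fold under the assumptions in step 4. The weakness is that the comparison named in Section 1.5.1, higher doses against 1500 mg, cannot be read from the planned table. If someone later derives it by dose at onset over the whole study, the final dose will have been observed about 3.8 times less often per week than the lower doses. The effect on reported rates depends on recall, on which the documents are silent. A clearer summary is worth adding, but nothing here invalidates the planned one. The mismatch between Section 8.14 and Appendix B is a separate, minor point.

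**What to change.** In Section 10.4, keep the planned table and add two summaries:

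- TEAEs by dose level received, restricted to the 21-day escalation periods, with participants who took at least one dose at that level as the denominator. These periods have nearly the same length and contact schedule. Note the Day 21 visit that closes Period 4, and show the number of periods cut short.
- Observation-period TEAEs reported separately, as events per participant-week and by dose at onset, because Section 3.2 allows dose changes in that period.

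State that adjusting for exposure does not correct for unequal contact frequency, so the two summaries should not be set against each other as rates. State also that the escalation comparison is descriptive: dose order is fixed, and participants who do not tolerate a dose do not go on to the higher ones.

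The cost is one extra table split and fewer weeks in the dose comparison. It uses data already collected.

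Separately, reconcile Section 8.14 with Appendix B by stating whether the Day 3 call applies in the observation period. This is a wording change in one place or the other.
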